4.3 Retesting

Laboratory values can be retested once during screening for LDL-C that is in the range of 65-69 mg/dL, or for triglycerides in the range of 401- 450 mg/dL.

4.4 Rescreening

Participants may be rescreened on one occasion only, following consultation with the Medical Monitor, after a minimum of 5 days have elapsed from a patient's last screening visit.

4.5 Withdrawal Criteria

Participation of a patient in this clinical study may be discontinued for any of the following reasons:

- The patient withdraws consent or requests discontinuation from the study for any reason.
- Occurrence of any medical condition or circumstance that exposes the patient to substantial risk and/or does not allow the patient to adhere to the requirements of the protocol.
- Any serious adverse event (SAE), clinically significant adverse event, severe laboratory abnormality, intercurrent illness, or other medical condition which indicates to the Investigator that continued participation is not in the best interest of the patient. Specific guidance for monitoring of patients and the withdraw of study drug is found in Section 8.1.
- Pregnancy.
- Requirement of prohibited concomitant medication.
- Patient failure to comply with protocol requirements or study-related procedures.

• Termination of the study by the Sponsor or the regulatory authority.

Patients are encouraged not to change their statin dose or use of ezetimibe during the study. If such occurs, they should not be withdrawn from the study.

If a patient withdraws prematurely from the study due to the above criteria or any other reason, study staff should make every effort to complete the full panel of assessments scheduled for the end of follow-up visit (Day 85). The reason for patient withdrawal must be documented in the electronic case report form (eCRF).

A patient will be considered lost to follow-up if the patient repeatedly fails to return for scheduled visits and is unable to be contacted by the clinical study site. In the case of patients lost to follow-up, attempts to contact the patient must be made and documented in the patient's medical records.

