5.6.2 Restricted Medications and/or Procedures

Patients are restricted from using any new prescription or over-the-counter cholesterol lowering medication. In addition, until completion of follow-up, change in the concurrent dose or discontinuation of statin/ezetimibe medication during the course of the study is prohibited unless deemed medically necessary by the Investigator (or designee) or the patient's medical care provider.

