6.5 Early Termination Visit and Withdrawal Procedures

The end of treatment for patients completing the study is the Day 85 visit. For patients who are withdrawn from the study prior to completion, all Day 85 procedures will be performed at an early termination visit. These procedures include the following:

- Perform full physical examination.
- Record vital signs and weight.
- Collect urine sample for urinalysis assessment.

- Perform urine pregnancy test.
- Collect blood samples for clinical safety chemistry panel, coagulation, and hematology assessments.
- Collect blood samples for fasting lipid panel assessment.
- Collect blood samples for fasting apolipoproteins and LDL-C (beta-quant).
- Collect blood samples for hsCRP, PCSK9, and fibrinogen analysis.
- Collect blood samples for anti-drug antibody analysis
- Collect blood samples for sparse PK, cytokine panel and complement activation analysis.
- Perform 12-lead ECG measurements.
- Record adverse events.
- Record concomitant medications.

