#### 3.1.2 Analysis Visits

Scheduled visits will be assigned to analysis visits as recorded on the case report form (CRF). Unscheduled and early termination visits will be assigned to analysis visits according to the following visit windows:

Analysis Visit	Target Analysis Day	Low Analysis Day	High Analysis Day
Day 8	8	2	11
Day 15	15	12	18
Day 22	22	19	25
Day 29	29	26	32
Day 36	36	33	39
Day 43	43	40	46
Day 57	57	47	71
Day 85	85	72	85 or End of Study (if Last
			Observation > Day 85)

Within an analysis visit window, the measurement from the visit closest to the defined target analysis day will be used. If there is more than one measurement with equal distance to the defined target analysis day, the latter will be used. If no visits occur within a visit window, the measurement for this visit will be treated as missing.

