# 3.4.1 Secondary Efficacy Endpoints Analyses

The PCSK9 and LDL-C will be listed and summarized using descriptive statistics by treatment group over the study period to describe absolute and percent changes from baseline.

The secondary endpoints of the study will be analyzed using analysis of covariance (ANCOVA) models to compare the mean percent change from baseline in LDL-C and PCSK9 approximately 28 days after the first injection (Day 29) and approximately 28 and 56 days after the second injection of study drug (Day 57 and Day 85) between treatment groups with placebo. This ANCOVA model will include treatment as a factor and baseline level as a covariate. The missing values will be imputed by last observation carried forward (LOCF) method.

Normality will be tested for the model residuals and the p-value from the Shapiro-Wilk test will be provided. If the residuals of this model are not normal, then non-parametric analyses (Wilcoxon rank- sum test) will be explored to compare the difference in median percent change between treatment groups.

The presentation of results will be the observed data and include the estimated means by treatment group, their standard errors, and the estimated differences in means between the patient treatments and corresponding 95% confidence intervals and p-values.

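### Protocol 4.5 lets patients be withdrawn from the study for prohibited medication or non-compliance alone, so LOCF can replace values, chiefly Day 85, that could have been observed

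*Protocol*

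**What the plan says.** Protocol 4.5 introduces its withdrawal list with "Participation of a patient in this clinical study may be discontinued for any of the following reasons". The list concerns participation in the study, not dosing alone. One entry is "Requirement of prohibited concomitant medication"; another is failure to comply with the protocol or its procedures. The entry on adverse events and laboratory abnormalities turns on the Investigator's view of the patient's best interest. These two entries carry no such condition.

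The same section treats a change of statin dose or ezetimibe differently: "If such occurs, they should not be withdrawn from the study". Section 5.6.2 also forbids such changes unless they are medically necessary, and it adds: "Patients are restricted from using any new prescription or over-the-counter cholesterol lowering medication". Section 5.6.3 allows other medically needed drugs.

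On what follows withdrawal, Protocol 6.5 says: "For patients who are withdrawn from the study prior to completion, all Day 85 procedures will be performed at an early termination visit". No text asks a withdrawn patient to attend the remaining Appendix A visits.

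SAP 3.1.2 assigns early-termination visits to analysis windows: "Within an analysis visit window, the measurement from the visit closest to the defined target analysis day will be used". It continues: "If no visits occur within a visit window, the measurement for this visit will be treated as missing". For the ITT ANCOVA of percent change in PCSK9 and LDL-C at Days 29, 57 and 85, SAP 3.4.1 says: "The missing values will be imputed by last observation carried forward (LOCF) method". An MMRM without imputation is optional, and the secondary analyses are repeated in the Per-Protocol Population.

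**The concern.** A patient who needs a new lipid drug, or who breaks a protocol rule, can usually still be measured. The protocol accepts this for statin and ezetimibe changes, which also alter LDL-C for a reason other than CIVI 007, but not for a new lipid drug. If such a patient is withdrawn, values that visits already on the schedule would have supplied are assumed instead, while the ITT analysis still counts the patient.

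Day 85 is the most exposed time point, because it is the only scheduled look at durability 8 weeks after the last dose. Protocol 1.8 says the PK and PD data will help set doses and regimen for Phase 2b and 3, and with 12 patients per arm each observed value counts.

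Scheduled safety laboratory tests stop at the same visit, and clinically significant laboratory abnormalities are one of the two primary endpoints. Events already found are still followed: Protocol 8.2 follows significant abnormalities until they resolve or stabilise, and 8.4 does the same for SAEs. What is lost is routine screening for new abnormalities.

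**Working it through.** Neither document gives a withdrawal rate, a waning rate or a power calculation (Protocol 9.2.4), so the plan has no figure of its own to reproduce. The check traces the rules and then does the arithmetic for one patient.

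**Inputs.** 12 patients per arm (Protocol 9.2.4). Injections on Days 1 and 29 (5.1). Secondary time points on Days 29, 57 and 85 (SAP 3.4.1). Windows: Day 29 = 26–32, Day 57 = 47–71, Day 85 = 72 onward (SAP 3.1.2). SAP 3.4.1 also says that the results presented will be the observed data, which sits awkwardly with LOCF; I take the explicit imputation rule to govern the ANCOVA.

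**Which values are lost.** Planned values per arm and analyte: 12 × 3 = 36. The Synopsis allows non-completers to be replaced. One replacement in the same arm, with both patients kept in ITT, gives 13 × 3 = 39.

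| Early-termination visit | Filled by LOCF | No replacement | One replacement |
|---|---|---|---|
| Days 2–25 | 29, 57, 85 | 3/36 = 8.3% | 3/39 = 7.7% |
| Days 26–46 | 57, 85 | 2/36 = 5.6% | 2/39 = 5.1% |
| Days 47–71 | 85 | 1/36 = 2.8% | 1/39 = 2.6% |
| Day 72 or later | none | 0 | 0 |

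**The losses do not weigh equally.** Protocol 3.2 and 5.2 describe Phase 1 lipid reductions as developing within about a week, stable to 4 weeks, and similar after single and multiple doses. A value carried to Day 29 once the effect has developed, or from Day 36 or 43 to Day 57 in a fixed-dose arm, should therefore be near the truth. Two limits apply. Those sections describe the time course of lipids, not of PCSK9. And the Day 57 argument assumes that the second injection is given; without it, Day 57 is 57 − 1 = 56 days after the only dose. Day 85 is 85 − 29 = 56 days after the last dose, beyond the 4 weeks described.

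**Up-titration arm.** An early-termination visit on Day 30, 31 or 32 lies 1, 2 or 3 days from the Day 29 target, against 0 for a visit held on Day 29, so the Day 29 value is used. If LOCF carries analysis-visit values (the SAP does not say), Day 57 then rests on a value that reflects only the lower first dose.

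**Direction.** If the effect wanes, a value carried to Day 85 overstates it. Persistence is also possible: PCSK9 in monkeys had not fully recovered after 8 weeks (Protocol 1.2.1), and the extended follow-up rule provides for LDL-C still below 80% of baseline at Day 85. In the up-titration arm the Day 57 effect can be understated. The sign is not determined.

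**Size.** Shift in the unadjusted arm mean = (w/n) × e, where w is the number of withdrawn patients, n the arm size, and e the carried value minus the value that would have been observed. Both w and e are assumptions.
- w = 1, n = 12: e = 10 gives 10/12 = 0.83 points; e = 20 gives 1.67; e = 40 gives 3.33.
- w = 1, n = 13: e = 10 gives 10/13 = 0.77; e = 20 gives 1.54.
- w = 2, n = 12: e = 10 gives 1.67; e = 40 gives 6.67.

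**The case against.** The case against is that this will seldom happen and matters little when it does. Withdrawal is optional. The medication ground is narrow: 5.6.2 mainly targets new cholesterol-lowering drugs, and 5.6.3 allows other needed drugs. Site staff give both doses (5.5.4), so non-compliance will often mean missed visits, which a rule on retention cannot fully cure. Lipid results after randomization are blinded to sites (5.3), which removes one prompt to add a lipid drug. The Per-Protocol repeat may already set such patients aside. The bias itself comes from LOCF, which is a separate choice.

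Most of this stands and limits the weight of the point. Two parts do not remove it. The Per-Protocol repeat drops the patient, so it cannot recover the values lost to ITT. And LOCF fills only what is missing; here the withdrawal rule helps create the gap.

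A reader might also infer that stopping study drug under 8.1, or being ineligible for the second injection, ends follow-up. The documents do not support that: 6.5 applies to withdrawal from the study, and 8.1 expects liver tests to continue after drug is stopped.

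**Conclusion.** The point holds as a modest, inexpensive design improvement. Section 4.5 permits an avoidable loss of secondary-endpoint data and routine safety laboratory data, and treats a new lipid drug differently from a statin or ezetimibe change without a stated reason. The loss matters most at Day 85 and, in the up-titration arm, at Day 57 when the last value precedes the effect of the second dose. Day 29, and Day 57 in the fixed-dose arms once the second dose is given, are less affected.

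Four stronger readings go beyond the text:
- That withdrawal is required: 4.5 only permits it.
- That 6.5 says in words that the remaining visits are cancelled: this is implied.
- That LOCF would inflate the effect of CIVI 007: the error can go either way.
- That safety follow-up ends altogether: event-driven follow-up continues.

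The size rests on assumptions: 0.83 points on an arm mean for one patient in 12 and a 10-point carried error, ignoring baseline adjustment. The endpoints affected by LOCF are secondary, in a study not sized by power.

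**What to change.** In Protocol 4.5 and 6.5, state that need for a prohibited medication, or non-compliance, is not by itself a reason to leave the study, and that these patients are asked to keep the Appendix A visits to Day 85, counted from Day 1. Whether they receive the second injection follows the existing Day 29 eligibility check. Leave every other ground in 4.5 as it is (consent, substantial risk, adverse event, laboratory or best-interest judgement, pregnancy, study termination), and leave the 8.1 criteria unchanged.

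In the SAP:
- Flag PCSK9 and LDL-C values taken after any post-randomization change in lipid-lowering therapy, whether a new drug or a statin or ezetimibe change. Keep them as observed in the ITT ANCOVA.
- Add one sensitivity analysis that excludes the flagged values without LOCF, for example the MMRM already described in 3.4.1. Setting them to missing within the ANCOVA would only have LOCF fill them again.
- In 3.3.1, report treatment discontinuation separately from study discontinuation. Section 3.6.1 already makes that split for adverse events, and 3.3.7 counts injections.

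The cost is a few sentences, one flag, one disposition item and one extra analysis. A few patients keep visits already planned for them, and some may still miss them. LOCF for patients who do leave the study is a separate issue that this change does not settle.

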5 STUDY TREATMENTS

5.1 Treatment Groups

All eligible patients will participate in the Screening Visit up to 21 days prior to Day 1. The Screening Visit will be their first study visit.

The Treatment Period will consist of two administrations of study drug. Eligible patients will be randomized on Day 1 in a 1:1:1:1 ratio to one of the following treatment groups:

- Group 1: cci mg CIVI 007 administered SC on Days 1 and 29
- Group 2: cci mg CIVI 007 administered SC on Day 1 followed by cci mg CIVI 007 administered SC on Day 29
- Group 3: mg CIVI 007 administered SC on Days 1 and 29
- Group 4: Placebo for CIVI 007 administered SC on Days 1 and 29

5.2 Rationale for Dosing

Standard antisense molecules have been demonstrated to scale allometrically between the mouse, monkey, and human based on body weight. Accordingly, with a NOAEL in monkeys of 30 mg/kg, the doses of and an average body weight of 60 kg) is > CCI - fold below the NOAEL.

More importantly, based on initial data from the ongoing FIH study and within the context of a limited experience, CIVI 007 appears to provide the expected pharmacologic profile associated with PCSK9 inhibition. CIVI 007 shows PCSK9 knockdown that begins around 12.5 mg with maximal inhibition of approximately 90% at mg. The efficacy profile includes robust, dosedependent reductions in atherogenic lipoproteins and lipids that begin within 1 week of administration and are stable out to 4 weeks after administration. Changes in lipoproteins and lipids after multiple doses are consistent with those after single doses.

There were no obvious drug-related safety findings in the dose range of 12.5 to a mg. Grade 1 ALT elevations appeared in both placebo and active doses with similar frequency. At higher doses, and based on higher levels of ALT increase, a signal of hepatotoxicity was apparent at 300 mg with a potential signal in one subject at 150 mg that was confounded with alcohol intake at the time of liver testing.

CIVI 007 therefore appears to have a favorable clinical profile at lower doses and these justify advancement to Phase 2a testing in this study.

5.3 Randomization and Blinding

Approximately 48 patients will be assigned randomly to placebo, comma CIVI 007, comma CIVI 007 followed by comma CIVI 007 or comma CIVI 007 in a 1:1:1:1 allocation ratio.

Throughout the study, study treatment will be administered in a double-blinded fashion for the Investigator, clinical staff, and patients. Only where required will key site staff (such as pharmacist) be unblinded throughout the study.

The following controls will be employed to maintain the double-blind execution of the study:

• The placebo solution will be identical in appearance to the CIVI 007 solution.

- The Investigator and other members of staff involved with the study will remain blinded.
- Lipid levels after randomization will be blinded to the study site.
- Appropriate firewalls will exist to prevent communication between the unblinded SRC and personnel involved in study execution.

5.4 Breaking the Blind

In order to manage patient safety (in the event of possible treatment-related SAEs or severe adverse events), the decision to unblind resides solely with the Investigator. Whenever possible, and providing it does not interfere with or delay any decision in the best interest of the patient, the Investigator will discuss the intended code-break with the study Medical Monitor. If it becomes necessary to break the code it will be done using the IRT and the date, time, and reason will be recorded in the patient's source data.

5.5 Drug Supplies

5.5.1 Formulation and Packaging

CIVI 007 for SC administration will be supplied by the Sponsor in vials packaged in a study drug kit (2 vials per kit). The placebo study drug (commercial grade sterile saline solution for SC administration) will also be supplied by the Sponsor.

Study drug will be packaged according to current Good Manufacturing Practice (GMP) and Good Clinical Practice (GCP) guidelines.

Study drug will be labeled according to the requirements of local law and legislation, as well as current GMP and GCP guidelines. Proof labels, detailing actual label text, will be available in the study files.

An unblinded pharmacist will prepare the appropriate study drug or placebo for blinded administration by the Investigator site.

5.5.2 Study Drug Preparation and Dispensing

The study drugs will be transferred from the pharmacy to the area where patients will be dosed by qualified clinical staff who will remain blinded to the treatment group.

5.5.3 Study Drug Administration

CIVI 007 and placebo are sterile solutions to be administered by SC injection.

Dosing is to be in the morning following an overnight fast:

- CIVI 007 (color colomg) is to be administered SC into the abdomen (or thigh or upper arm, if necessary) from a solution at 150 mg/mL (colomg per colomL vial).
- Placebo is to be administered SC into the abdomen (or in thigh or upper arm, if necessary).
 The volume of injection will be randomly assigned to match one of the two active CIVI 007 doses.

Note: For the second dose of CIVI 007 or placebo administration, the investigators should try to avoid using the same injection site area as the first dose. For other permitted concomitant

medications administered subcutaneously, do not administer in same injection site area as the study drug, for at least 2 weeks after the last dose of study drug.

5.5.4 Treatment Compliance

The following measures will be employed to ensure treatment compliance:

 All doses will be administered by and under the supervision of suitably qualified study site staff.

5.5.5 Storage and Accountability

Both CIVI 007 and placebo will be stored at the study site, according to the instructions on the label, in a location that is locked with restricted access.

The unblinded pharmacist will maintain an accurate record of the receipt of CIVI 007 and placebo vials received. In addition, an accurate drug disposition record will be kept, specifying the amount dispensed to each patient and the date of dispensing. This drug accountability record will be available for inspection at any time. At the completion of the study, the original drug accountability record will be available for review by the Sponsor upon request.

Used and empty dose kits will be discarded upon satisfactory completion of the compliance and accountability procedures by study CRO personnel monitoring the study. Any unused or partially used kits will be retained until completion of the study.

At the completion of the study, all unused CIVI 007 kits and vials will be returned to the Sponsor or disposed of by the study site, per the Sponsor's written instructions.

5.6 Prior and Concomitant Medications and/or Procedures

5.6.1 Excluded Medications and/or Procedures

Once eligibility is determined, and until study completion, patients are to be counseled from use of any new, or change in dose, of any prescription or nonprescription medications/products. Specific attention is to be paid to maintaining the concurrent dose of statin/ezetimibe therapy during the course of the study.

5.6.2 Restricted Medications and/or Procedures

Patients are restricted from using any new prescription or over-the-counter cholesterol lowering medication. In addition, until completion of follow-up, change in the concurrent dose or discontinuation of statin/ezetimibe medication during the course of the study is prohibited unless deemed medically necessary by the Investigator (or designee) or the patient's medical care provider.

5.6.3 Allowed Medications and/or Procedures

Except as noted in restricted medications, and if medically warranted and deemed necessary by the Investigator (or designee) or the patient's medical care provider, concurrent medication is to be added or doses changed as needed given the patient's prior consent to its use.

5.6.4 Documentation of Prior and Concomitant Medication Use

Any medication taken by a patient during the course of the study and the reason for its use will be documented in the source data. For patients not taking a lower than recommended statin therapy, the reason should be documented in the CRF.

5.7 Dietary and Lifestyle Restrictions

5.7.1 Diet

Most study visits require measurement of fasting lipids. Those study visits requiring lipid measurement should be following an overnight fast by the patient (10 hours ± 2 hours).

In addition, on Day 1 and Day 29, patients will be fasted overnight (10 ± 2 hours) prior to study drug administration and until 3 hours post-dose, after which a meal will be provided by study staff (lunch times will be staggered as needed between patients to ensure this 3-hour interval in each case). Patients may consume water ad libitum during the days of study drug administration.

At all other times during the study, patients are to follow their normal dietary pattern and may consume water ad libitum.

Consumption of alcohol will not be permitted the day immediately prior to and days of study drug administration. Alcohol intake will be limited to a maximum of 2 units/day on all other days, from screening through the final Follow-up Visit.

